A number of studies and reports support the short-term use of topical corticosteroids known to be potent anti-inflammatory agents in the treatment of patients with DED ([Avunduk et al, 2003](#); [DEWS II Report 2017](#); [Pflugfelder et al, 1999](#); [Yang et al, 2006](#)). While topical ophthalmic corticosteroids are approved by the Food and Drug Administration (FDA) for corticosteroid-responsive inflammatory conditions of the conjunctiva, cornea, and anterior globe, they are generally only recommended for short-term use, as prolonged use may result in adverse ocular events, including elevated Intraocular Pressure (IOP), cataracts, and ocular infection ([Becker, 1964](#); [Bowling and Russell, 2011](#); [Dinning, 1976](#)). Short-term corticosteroid therapy can serve as both an important adjunct to existing chronic therapies (e.g., artificial tears) and can also be used to address environmental and iatrogenic induced breakthrough periods of increased ocular surface inflammation ([Becker, 1964](#); [Behrens et al, 2006](#)).

Pflugfelder and colleagues ([Pflugfelder, 2004](#)) demonstrated that a topical corticosteroid may achieve the objective of a short-term treatment of acute exacerbations of DED signs or symptoms. They evaluated loteprednol etabonate ophthalmic suspension (0.5%) dosed 4 times daily versus placebo for the treatment of DED in patients with delayed tear clearance. In patients with at least moderate clinical inflammation, significant differences in clinical signs (nasal and tarsal hyperemia) between groups were observed as early as Week 2 and persisted

through Week 4 of the study. In addition, the improvement in the redness Visual Analog Scale (VAS) score was consistently 20% better in the loteprednol-treated patients compared with the Vehicle-treated patients.

AxeroVision, Inc. intends to develop AXR-270 Cream, for the treatment of MGD secondary to posterior blepharitis. Study AXR201901 will evaluate the safety and tolerability of AXR-270 Cream in subjects with lid margin inflammation (as characterized by eyelid margin hyperemia) due to Meibomian Gland Dysfunction. Additional information about AXR-270 Cream, including nonclinical pharmacology study results, and potential risks and benefits to human subjects, is found in the Investigator's Brochure.

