2. TRIAL OBJECTIVES AND PURPOSE

2.1. OBJECTIVE

The primary objective of this study is to evaluate the safety and tolerability of two concentrations (0.2% and 2.0%) of AXR-270 Cream in treating posterior blepharitis associated with MGD.

The secondary objective is to evaluate the efficacy of AXR-270 Cream in treating signs and symptoms of posterior blepharitis associated with MGD.

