9.5. ANALYSIS OF SAFETY

Analysis of safety data will be presented for all subjects in the Safety Population. AEs will be coded using Medical Dictionary for Regulatory Activities (MedDRA, most current version) and categorized by system organ class using preferred terms. AEs will be tabulated by treatment group with respect to their Severity and relationship to the IP. Ophthalmoscopy findings will be summarized descriptively. IOP measurements, BCVA, dilated ophthalmoscopy, and slit-lamp biomicroscopy (including external eye exam) will be summarized as safety outcomes.

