16. APPENDICES

APPENDIX 1: SCHEDULE OF EVENTS

	Visit 1	Visit 2	Visit 3	Visit 4	Visit 5
Procedures	Day minus 14 (±2 days)	Day 1	Day 8 (±2 days)	Day 15 (±3 days)	Day 22 (±3 days)
	Screening	Randomization	Week 1	Week 2	Week 3
	Equalization Period	Treatment Period			Study Termination
Informed Consent	X				
Inclusion/Exclusion Criteria	X	X			
Randomization Criteria		X			
Demographics, Systemic and Ocular Medical History	X				
Subject-rated Symptom Assessments VAS (Eye Discomfort and Eye Dryness)	X	X	X	X	X
OSDI	X	X	X	X	X
Modified BLISS	X	X	X	X	X
Concomitant Medication Query	X	X	X	X	X
Adverse Event Query		X	X	X	X
UPT	X				X
BCVA	X	X	X	X	X
Slit-lamp Biomicroscopy (including External Eye Exam)	X	X	X	X	X
TBUT	X	X	X	X	X
FCS	X	X	X	X	X
Investigator-rated assessment of signs of MGD: Total MGD Score Eyelid margin vascularity Bulbar conjunctival hyperemia	X	X	X	X	X
LGS ^a	X	X	X	X	X
Unanesthetized Schirmer Test	X	X	X	X	X
IOP	X	X	X	X	X
Dilated Ophthalmoscopy	X				X
Safety Lab Draw		X			X
Dispense Investigational Product for Home Administration		X			
Dispense Daily Dosing Diaries / IP Comfort Assessment Questionnaire		X			
In Clinic Administration of Investigational Product, IP Comfort Assessment Questionnaire and Instruction on Proper Administration ^b		X			
Collect/Review Daily Dosing Diary, IP Comfort Assessment Questionnaire and Investigational Product			X ^c	X	X
Study Termination					X

Key: OSDI=Ocular Surface Disease Index; TBUT=Tear Break up Time; BLISS= BLEpharItIS Symptom; AE=Adverse Event; UPT=Urine Pregnancy Test; IOP=Intraocular Pressure; VAS=Visual Analog Scale; BCVA=Best Corrected Visual Acuity; FCS=Fluorescein Corneal Staining; LGS=Lissamine Green Staining; IP=Investigational Product.

^aOnly to be performed at a subset of sites

^bIncludes dosing video on proper administration of IP

^cIP will not be collected at Visit 3

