APPENDIX 5: SLIT LAMP BIOMICROSCOPY

The biomicroscopy exam should be performed with the slit-lamp using a beam width and intensity that provide optimal evaluation of the anterior segment.

This procedure will be performed in the same manner for all subjects observed at the Investigator's site. The site will record all ABNORMAL findings in the source document and the investigator will evaluate the ABNORMAL findings as Non-Clinically Significant (NCS) or Clinically Significant (CS). CS and NCS ABNORMAL findings will be recorded in the source documentation. However, only ABNORMAL CS descriptions will be captured in the eCRF.

Lashes

0 = Normal

1 = Abnormal

Eyelid

Edema

0 = Normal, no swelling of the lid tissue

1 = Abnormal

Skin

0 = Normal, including but not limited to thinning, pigment changes, dermatitis

1 = Abnormal

Conjunctiva

Edema

0 = Normal, no swelling of the conjunctiva

1 = Abnormal

Palpebral Conjunctival Erythema

0 = Normal, no redness of the conjunctiva

1 = Abnormal

Cornea

Infiltrates

0 = Absent

1 = Present

Endothelial Changes

0 = Normal, None

1 = Abnormal, pigment, keratoprecipitates, guttata

Edema

0 = Normal, None, transparent and clear

1 = Abnormal

Anterior Chamber

Cells

0 = Normal, No cells seen

1 = Abnormal (+ to +++ cells)

Flare

0 = Normal, No Tyndall effect

1 = Abnormal, Tyndall beam in the anterior chamber

Lens Pathology

0 = Normal, no opacity in the lens

1 = Abnormal, existing opacity in the lens; aphakic or pseudophakic eyes or other abnormal findings

Sclera

0 = Normal

1 = Abnormal

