4.8.4. Intraocular Pressure

The actual value and change from baseline to each on study evaluation will be summarized for intraocular pressure (mmHg) for the study eye and non-study eye by treatment group. Counts and percentages of subjects by study eye and non-study eye with elevations in IOP at any point in the study will also be provided for the following elevation categories:

- IOP increase from baseline ≥ 10 mmHg

Sponsor:	AxeroVision, Inc.		
Protocol:	AXR201901		
Document Version No.:	1.1	Document Date:	26-OCT-2020

- Absolute IOP value >25 mmHg
- Absolute IOP value >30 mmHg

If a subject has an absolute IOP value >30 mmHg, they will be counted in both categories of ‘Absolute IOP value >25 mmHg as well as in ‘Absolute IOP value >30 mmHg’. All intraocular pressure data will be provided in data listing with elevation categories flagged.

4.8.5. **Best Corrected Visual Acuity**

The actual value and change from baseline to each on study evaluation will be summarized for the calculated logMAR score for the study eye and non-study eye by treatment group.

All BCVA data will be provided in data listings.

4.8.6. **Slit-lamp Biomicroscopy and External Eye Exam**

Slit-lamp biomicroscopy and external eye exam findings will be summarized descriptively, including the number and percent of subjects with normal/not present and abnormal/present results for lashes, eyelid edema, eyelid skin, conjunctival edema, palpebral conjunctival erythema, corneal infiltrates, corneal endothelial changes, and corneal edema results at baseline and each study visit by treatment group and study or non-study eye.

All slit-lamp biomicroscopy and external eye exam data will be provided in data listings.

4.8.7. **Urine Pregnancy Test and Concomitant Medications**

All urine pregnancy and concomitant medication data will be provided in data listings.

4.8.8. **IP Comfort Assessment**

The actual value and change from baseline to each on study evaluation will be summarized for the IP Comfort Assessment by treatment group.

All IP Comfort Assessment data will be provided in data listings.

Statistical Analysis Plan Template

Sponsor:	AxeroVision, Inc.		
Protocol:	AXR201901		
Document Version No.:	1.1	Document Date:	26-OCT-2020

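### The SAP's slit-lamp summary names 8 of the 12 graded items; anterior-chamber cells, flare, lens and sclera are left to listings with no by-arm count

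*SAP*

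**What the plan says.** Protocol 2.1 puts safety first: "The primary objective of this study is to evaluate the safety and tolerability of two concentrations (0.2% and 2.0%) of AXR-270 Cream". Slit-lamp biomicroscopy with external eye exam is a listed safety endpoint (Protocol 3.1.1), and Appendix 1 schedules it at Visits 1 to 5. Protocol 9.5 commits to reporting it and excepts no item: "IOP measurements, BCVA, dilated ophthalmoscopy, and slit-lamp biomicroscopy (including external eye exam) will be summarized as safety outcomes".

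Protocol Appendix 5 defines the examination as a set of 0/1 grades. They include anterior-chamber cells ("0 = Normal, No cells seen"), anterior-chamber flare ("1 = Abnormal, Tyndall beam in the anterior chamber"), the lens ("1 = Abnormal, existing opacity in the lens; aphakic or pseudophakic eyes or other abnormal findings") and the sclera.

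SAP 4.8.6 plans numbers and percentages of normal and abnormal results, at baseline and each visit, by treatment group and study or non-study eye, for these items: "lashes, eyelid edema, eyelid skin, conjunctival edema, palpebral conjunctival erythema, corneal infiltrates, corneal endothelial changes, and corneal edema". It sends all slit-lamp data to listings. Table 14.4.2.5 in SAP 7.1 carries a generic title and names no items. SAP Section 5, on changes to planned analyses, does not mention the slit lamp.

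**The concern.** The SAP list follows the order of Appendix 5 and stops after the cornea. What comes next in the appendix is absent: anterior chamber, lens and sclera. A programmer working from SAP 4.8.6 would build a table without them, and the report would give no by-arm count of those examination grades for the roughly 126 subjects. A listing lets a reader find individual cases but does not set the active arms against Vehicle.

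The items are relevant to this product. The protocol's introduction says of topical ophthalmic corticosteroids that "prolonged use may result in adverse ocular events, including elevated Intraocular Pressure (IOP), cataracts, and ocular infection". Subjects are told to keep the cream out of the eye, and the diary asks about spread into the eye, so some ocular exposure is anticipated. Current or past iritis or uveitis is excluded (exclusion 1), so cells or flare after baseline would be informative.

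A second, smaller issue concerns the form of the summary. Counts of abnormal results at each visit do not separate new findings from old ones.

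**Working it through.** The plan states no figure to reproduce. The check is a count of items, a search for the missing items elsewhere in the SAP, and a look at what per-visit counts can show.

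**1. Item count, Appendix 5 against SAP 4.8.6**

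| Structure (items) | Graded in Appendix 5 | Named in SAP 4.8.6 |
|---|---|---|
| Lashes | 1 | 1 |
| Eyelid (edema; skin) | 2 | 2 |
| Conjunctiva (edema; palpebral erythema) | 2 | 2 |
| Cornea (infiltrates; endothelium; edema) | 3 | 3 |
| Anterior chamber (cells; flare) | 2 | 0 |
| Lens | 1 | 0 |
| Sclera | 1 | 0 |
| **Total** | **12** | **8** |

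Omitted: 12 − 8 = 4 items, and 4/12 = 33% of the checklist. Three of the four are intraocular; the sclera is not.

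**2. Is the gap filled elsewhere?**

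- SAP 4.8.3 (dilated ophthalmoscopy) covers retina, optic nerve and cup-to-disc ratio. It does not cover the lens or anterior chamber, and the examination is done only at Visits 1 and 5.
- SAP 4.8.4 and 4.8.5 cover IOP and BCVA.
- Table 14.4.2.5 adds no items. Listing 16.2.9.4 holds the slit-lamp data by subject.
- SAP 4.8.1 tabulates ocular treatment-emergent adverse events by arm, with severity and relationship. A lens or anterior-chamber finding reported as an adverse event would appear there.
- The retained endothelial item counts keratoprecipitates as abnormal (Appendix 5), so one sign of intraocular inflammation is still tabulated.

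So the by-arm count of the four examination grades is missing, but other by-arm evidence on the same harms is not.

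**3. What per-visit counts show**

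For one item and arm, with the same eyes examined at both times:

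abnormal at visit t = abnormal at baseline + newly abnormal − resolved.

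The change between the baseline and visit columns is therefore newly abnormal minus resolved. Net change is visible; new findings offset by resolved ones are not. This matters most for lid and conjunctival items in a blepharitis population, where both can occur. For the lens, abnormal includes existing opacity and pseudophakia, and penetrating intraocular surgery is barred only within 90 days of screening, so eyes already abnormal can enter. Elsewhere the SAP does use baseline: laboratory data get shift tables (4.8.2), and IOP and BCVA get change from baseline (4.8.4, 4.8.5).

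**4. Are the data available?**

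Appendix 5 says that abnormal findings of both kinds go into the source document, but that only descriptions of clinically significant abnormalities go into the eCRF. The planned normal/abnormal counts for the other eight items suggest that the 0/1 grades themselves are captured. The documents do not say so for the four omitted items.

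**The case against.** The best defense is that little is lost. Clinically important events would be reported as adverse events and tabulated by arm, keratoprecipitates remain in the slit-lamp table, and IOP, BCVA, retina and optic nerve are all summarized. This stands. A reader might infer that part of the primary safety objective goes unanalyzed, or that the report will hold no by-arm information on intraocular inflammation. The documents support neither reading.

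The cataract link is also weaker than it looks. The protocol ties cataract to prolonged use and contrasts that with short-term use. Treatment here is about 21 days, on eyelid skin, and the documents imply rather than state that AXR-270 is a corticosteroid. It would be wrong to infer that a likely cataract signal is being missed. The anterior-chamber items do not depend on this argument.

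The wording can be read generously. SAP 4.8.6 introduces its counts as included in a descriptive summary, no table shell is shown, and SAP Section 5 lists only additions, so its silence says little about intent. But the item list itself is closed, and nothing in the SAP commits to the other four. SAP 1.1 also says that the document sets out differences from the protocol's planned analyses.

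On new-onset counts, the protocol promises none, and the baseline column already shows net change. A reader might infer that abnormalities at entry hide all new ones; only offsetting within-eye changes are hidden. The request is an improvement in the summary, not the repair of a broken commitment.

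**Conclusion.** The point holds as a gap in the SAP's slit-lamp summary. Four of 12 graded items (33%), namely anterior-chamber cells, anterior-chamber flare, lens pathology and sclera, have no by-arm tabulation although Protocol 9.5 promises a summary without exception. The 33% is a share of checklist items, not of safety information. The examination is scheduled at five visits, but the table would cover four timepoints: baseline, normally Visit 2, and Visits 3, 4 and 5.

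The conclusion rests on reading the SAP 4.8.6 list as closed and on the absence of a table shell that adds the items. Few lens findings are to be expected. The change is still worth making, because safety is the primary objective and the by-arm comparison costs almost nothing.

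**What to change.** 1. Confirm that the eCRF captures the 0/1 grades for all 12 items, and not only descriptions of clinically significant abnormalities. If it does not, say so in the SAP and limit the summary to what is collected.
2. Add anterior-chamber cells, anterior-chamber flare, lens pathology and sclera to SAP 4.8.6 and Table 14.4.2.5, at baseline and each post-baseline visit. If the sponsor prefers to keep them in listings only, declare and justify that in SAP Section 5.
3. For all 12 items add, by arm and by study/non-study eye, the number and percent of eyes normal at baseline that become abnormal at any post-baseline visit. The denominator is eyes normal at baseline with at least one post-baseline examination. State that a 0/1 lens grade cannot show progression of an existing opacity.

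The cost is SAP wording and more rows in one existing table: 4 items × 4 timepoints × 2 eye categories = 32 item-by-visit summaries, plus 12 items × 2 eye categories = 24 new-onset summaries, each across the three treatment columns. If step 1 is confirmed, no new data are needed.

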3. TRIAL DESIGN
3.1. STUDY ENDPOINTS

3.1.1. Safety Endpoints

- Adverse events (AE)
- Best corrected visual acuity (BCVA)
- Slit-lamp biomicroscopy and external eye exam
- Intraocular pressure (IOP)
- Dilated ophthalmoscopy
- Safety Labs (Hematology, clinical chemistry, and urinalysis)

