APPENDIX 14: DAILY DOSING DIARY

Subjects will be asked to record each day the following information related to administration of IP:

- Date
- Time of Administration
- IP Comfort Assessment (Below)

Each evening, the subject will be asked to respond to the following questions:

Investigational Product Comfort Assessment	
Overall tolerance of Investigational Product	1-Excellent 2-Good 3-Fair 4-Poor
Concern about the following immediately after application:	
Eyelid Redness	1-No Concern 2-Slightly Concerned 3-Moderately Concerned 4-Very Concerned
Eyelid Stinging	1-No Concern 2-Slightly Concerned 3-Moderately Concerned 4-Very Concerned
Eyelid Burning	1-No Concern 2-Slightly Concerned 3-Moderately Concerned 4-Very Concerned
Heavy Eyelid Sensation	1-No Concern 2-Slightly Concerned

	
3-Moderately Concerned
 
4-Very Concerned

Sticky Feeling in Eye	
1-No Concern
 
2-Slightly Concerned
 
3-Moderately Concerned
 
4-Very Concerned

Spreading into Eye	
1-No Concern
 
2-Slightly Concerned
 
3-Moderately Concerned
 
4-Very Concerned

Oily Feeling in Eye	
1-No Concern
 
2-Slightly Concerned
 
3-Moderately Concerned
 
4-Very Concerned

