2.5.3. Safety Variables

Safety variables include:

- Adverse Events (AEs)
- Best Corrected Visual Acuity (BCVA)

Statistical Analysis Plan Template

Sponsor:	AxeroVision, Inc.		
Protocol:	AXR201901		
Document Version No.:	1.1	Document Date:	26-OCT-2020

-
- Slit-lamp biomicroscopy and external eye exam
 - Intraocular Pressure (IOP)
 - Dilated Ophthalmoscopy
 - Safety labs (hematology, clinical chemistry, and urinalysis)

Statistical Analysis Plan Template

Sponsor:	AxeroVision, Inc.		
Protocol:	AXR201901		
Document Version No.:	1.1	Document Date:	26-OCT-2020

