14.4.2.5	Slit-lamp Biomicroscopy and External Eye Exam by Study/Non-study Eye – Safety Set
14.4.2.6	IP Comfort Assessment – Safety Set

* Topline table

Statistical Analysis Plan Template

Sponsor:	AxeroVision, Inc.		
Protocol:	AXR201901		
Document Version No.:	1.1	Document Date:	26-OCT-2020

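### The tolerability questionnaire is not a named endpoint, its planned change from baseline cannot be computed, and no table counts subjects who ever gave a poor rating

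*SAP*

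**What the plan says.** Protocol 2.1 sets the aim: "The primary objective of this study is to evaluate the safety and tolerability of two concentrations (0.2% and 2.0%) of AXR-270 Cream". SAP 1.2 repeats it.

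The IP Comfort Assessment (Protocol Appendix 14) has one overall tolerance item and seven concern items, each scored 1 (best) to 4 (worst). It is completed in the clinic shortly after the first dose (Protocol 5.1.2) and then at home with the dosing diary: "Each evening, the subject will be asked to respond to the following questions".

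Protocol 3.1.1 lists six safety endpoints, ending with "Safety Labs (Hematology, clinical chemistry, and urinalysis". SAP 2.5.3 lists the same six. Comfort is in neither list, nor in Protocol 8.1 or 9.5.

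SAP 4.8.8 gives the analysis: "The actual value and change from baseline to each on study evaluation will be summarized for the IP Comfort Assessment by treatment group". It adds that the data will be listed. SAP 7.1 plans one table, 14.4.2.6, "IP Comfort Assessment – Safety Set". It is not marked as a topline table, whereas the two treatment-emergent AE overviews and the table of IOP values are.

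**The concern.** A reader of the report will want to know what share of subjects on each concentration, compared with vehicle, found the cream hard to tolerate at any time. The planned summary looks at one evaluation after another. A subject who gives the worst rating early and stops is visible only in the early summaries. A subject with a few bad days among many good ones is counted on those days but never identified as one affected person. Half of the planned sentence also depends on a baseline that does not exist.

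At stake is whether tolerability can be read subject by subject from a prespecified table. Otherwise it must be pieced together from listings after unmasking.

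**Working it through.** The documents give no tolerability rate, dropout rate or sample-size calculation, so there is no stated figure to reproduce. The check is a comparison of passages followed by an illustration on assumed counts.

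**1. Can change from baseline be computed?**
- SAP 4.2.1 takes as baseline the last value obtained before the first dose.
- Protocol 5.1.2 places the first comfort rating about two minutes after that dose. Appendix 1 schedules none earlier.
- No subject therefore has a comfort baseline, and the change is undefined for everyone.

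**2. What is an evaluation?** With dosing from Day 1 to Day 21 there are 21 doses (Protocol 3.2: no dose on Day 22; the Visit 5 window of 3 days either way moves this). One rating set per dose gives 8 items × 21 = 168 ratings per subject. SAP 4.8.8 does not say whether these are summarised by day, diary week or visit.

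**3. What happens to subjects who stop?** Three readings are open:
- observed cases only;
- the general LOCF rule in SAP 4.2.8, which is not limited to efficacy, although SAP 4.6 uses LOCF as a sensitivity analysis for study eye/eyelid values and SAP 7.1 lists no comfort sensitivity table;
- the missing-data category that SAP 4.2.1 gives to categorical variables. The wording of SAP 4.8.8 suggests a continuous summary, but does not settle it.

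**4. Does the SAP count subjects elsewhere?** Yes. SAP 4.8.4 counts subjects with raised IOP at any time in the study. SAP 4.8.1 counts each subject once for AEs, at the most intense or most related occurrence. Comfort has no counterpart.

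**5. Illustration (all counts assumed except the arm size of about 42).** Four subjects give the worst rating in week 1 and stop. No continuing subject gives it at the last evaluation. In the right-hand column, four others gave it once and recovered.

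| Summary | No transient cases | Four transient cases |
|---|---|---|
| Last evaluation, observed cases | 0/38 = 0% | 0/38 = 0% |
| Last evaluation, missing category | 0/42 poor, 4/42 missing | 0/42 poor, 4/42 missing |
| Last evaluation, LOCF | 4/42 = 9.5% | 4/42 = 9.5% |
| Subjects ever affected | 4/42 = 9.5% | 8/42 = 19.0% |

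The exact (Clopper-Pearson) 95% intervals for the last row are 2.7% to 22.6% and 8.6% to 34.1%. With 2 to 8 stoppers and no transient cases, the ever-affected share runs from 2/42 = 4.8% to 8/42 = 19.0%, while the observed-case figure stays at 0%.

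**6. Why by-time rates cannot stand in.** Suppose 5% of ratings are poor on every day (assumed). If they always come from the same subjects, 5% are ever affected. If days are independent, the share is 1 − 0.95^21 = 65.9%. At 2% per day the range is 2% to 1 − 0.98^21 = 34.6%. These are arithmetic bounds for any repeated rating, not predictions for this trial; they show only that the by-time table cannot tell the two situations apart.

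**The case against.** The strongest reply is that tolerability is not left to this questionnaire. AEs are reported by subject incidence, severity and relationship (SAP 4.8.1). Slit-lamp examination covers eyelid edema and skin (SAP 4.8.6). Treatment discontinuations and their reasons are tabulated by arm (SAP 4.4), and AEs leading to withdrawal are listed. Burning bad enough to stop treatment should surface there. Comfort has its own section under the safety analyses, a Safety Set table and listings, and diaries are collected at early termination, so no data are lost.

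Much of this stands. A reader might infer that comfort is the only tolerability measure, or that per-subject incidence is never reported. The documents support neither: comfort is the only dedicated questionnaire, and the missing incidence concerns comfort ratings alone.

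Three gaps remain:
- Protocol 8.3 elicits AEs with open, non-leading questions, and no rule turns a poor diary rating into an AE.
- Discontinuation reasons miss subjects who continue despite poor ratings, and the slit-lamp items do not record stinging or burning.
- Listings allow a later derivation, but the choice of summary would then follow unmasking.

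It is also fair to say that the by-time summary has value, since it shows whether tolerability improves or worsens with use. It should be kept and supplemented.

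**Conclusion.** The point holds as a gap in specification. Three parts rest on the text alone: comfort is in neither endpoint list, its change from baseline cannot be computed, and no worst-rating or any-time count per subject is planned for it.

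The loss of early stoppers is possible, not established. A reader might infer that they certainly vanish, or that the result is biased towards good tolerability in the arm that loses more subjects. That would need both observed-case handling and dropout driven by intolerance. The SAP does not settle the first, and the documents give no rate for the second. The stoppers' early ratings would in any case appear in the early summaries.

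The size is therefore conditional. Under the assumed 4 stoppers in 42, the final summary could read 0 of 38 against 9.5% ever affected. LOCF would restore those four but would still miss transient cases. The data are being collected and no other analysis is affected, so this is a correction worth making before unmasking rather than a flaw that undermines the study.

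**What to change.** 1. Name the IP Comfort Assessment as a tolerability variable in Protocol 3.1.1 and SAP 2.5.3.
2. In SAP 4.8.8 and Table 14.4.2.6, drop change from baseline. Define the evaluation unit, for example the first dose and then each diary week, and keep category counts by time.
3. Add, per item and arm with all dosed subjects as denominator: each subject's worst rating; the number and percent ever rated 3 or 4; and, for subjects who discontinue IP, the last rating before stopping.
4. Report the number of diary days rated alongside, because the chance of ever giving a poor rating depends on exposure and early stoppers have fewer days.
5. State whether LOCF or the missing-data category applies to the by-time counts.

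The cost is endpoint-list and SAP wording and one redesigned table. No new data are needed: the diaries already hold the ratings and are collected at early termination (Protocol 5.1.7).
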